[figure not shown]

Version Number: 1.0 Version Date: 18Dec2018

AnaptysBio Inc. PROTOCOL ANB020-004 Page 8 of 19

Figure 14 4 2 1 Waterfall plot: Change from Baseline in Peripheral Eosinophil Count on Day 22 – Pharmacodynamic Analysis Set

Programming Note: This is graph is only for representation purpose Y axis should have the % change from baseline, X-axis should have the treatments

Figure 14 4 2 2 Waterfall plot: Change from Baseline in Peripheral Eosinophil Count on Day 127/ET – Pharmacodynamic Analysis Set

Programming note: The abive layout should be followed

Version Number: 1.0 Version Date: 18Dec2018

[figure not shown]

AnaptysBio Inc. PROTOCOL ANB020-004 Page 9 of 19

Figure 14 4 1 1

Mean (±SD) Serum Concentration Time Profile of ANB020 for IV infusion – Safety Analysis Set

Linear Scale

End of infusion (EOI) was approximately 1 hour after the start of infusion and is plotted as 1 hour

SD = standard deviation

<Note: Plot is for example. Actual plot will have x- and y-axes and time points modified according to actual study data.>

Figure 14 4 1 1 (Cont'd)
Mean (±SD) Serum Concentration Time Profile of ANB020 for IV infusion – Pharmacokinetic Analysis Set

[figure not shown]
Version Number: 1.0 Version Date: 18Dec2018

CONFIDENTIAL

AnaptysBio Inc. PROTOCOL ANB020-004 Page 10 of 19

Semi-logarithmic scale

End of infusion (EOI) was approximately 1 hour after the start of infusion and is plotted as 1 hour

SD = standard deviation

<Note: Plot is for example. Actual plot will have x- and y-axes and time points modified according to actual study data.>

Version Date: 18Dec2018

1.0

[figure not shown]
Version Number:

CONFIDENTIAL

AnaptysBio Inc. PROTOCOL ANB020-004 Page 11 of 19

Figure 14 4 1 2 Individual Serum Concentration Time Profile of ANB020 for IV infusion - Safety Analysis Set Patient 1 Linear Scale

<Programming Note: Present all the patients. A linear and semi-log plot will be prepared for each subject > <Note: Plot is for example. Actual plot will have x- and y-axes and time points modified according to actual study data.>

\\ieedc-vnasc01\biosdata\AnaptysBio\ANB020\CYA74392\Biostatistics\Documentation\SAP\Final\20181218 Document: Author:

Version Number: 1.0 Version Date: 18Dec2018

[figure not shown]
153

29 June 2020

AnaptysBio Inc. PROTOCOL ANB020-004 Page 12 of 19

 $Figure~14~4~1~2~(Cont'd)\\ Individual~Serum~Concentration~Time~Profile~of~ANB020~for~IV~infusion-Safety~Analysis~Set\\ Patient~1$

Semi-logarithmic scale

[figure not shown]
<Programming Note: Present all the patients. A linear and semi-log plot will be prepared for each subject >

<Note: Plot is for example. Actual plot will have x- and y-axes and time points modified according to actual study data.>

Version Number: 1.0 Version Date: 18Dec2018

AnaptysBio Inc. PROTOCOL ANB020-004 Page 13 of 19

Figure 14 4 2 1 Mean (±95% CI) Eosinophil Count-time Profiles - Pharmacodynamic Analysis Set

CI = confidence interval

<Note: Plot is for example Actual plot will have x- and y-axes and time points modified according to actual study data >

Version Number: 1.0 Version Date:

18Dec2018

CONFIDENTIAL

Clinical Study Report ANB020-004 - Original

[figure not shown]

Figure Shells

AnaptysBio Inc. PROTOCOL ANB020-004 Page 14 of 19

Version Number:

1.0

Figure 14 4 2 2

Mean (±95% CI) Change from Baseline Eosinophil Count-time Profiles – Pharmacodynamic Analysis Set

A plot similar to Figure 14 4 2 1 will be presented for change from baseline values

[figure not shown]
Document: \\ieedc-vnasc01\\biosdata\AnaptysBio\ANB020\CYA74392\Biostatistics\Documentation\SAP\Final\20181218 Author:

Version Date: 18Dec2018 29 June 2020 156

AnaptysBio Inc. PROTOCOL ANB020-004 Page 15 of 19

Figure~14~4~2~3 Mean ($\pm 95\%$ CI) Concentration-time Profiles for Serum Cytokines – Pharmacodynamic Analysis Set

CI = confidence interval

<Note: Plot is for example Actual plot will have x- and y-axes and time points modified according to actual study data

[figure not shown]
Version Date: 18Dec2018

1.0

Version Number:

CONFIDENTIAL

Clinical Study Report ANB020-004 - Original

AnaptysBio Inc. PROTOCOL ANB020-004 Figure Shells Page 16 of 19

Figure 14 4 2 4

Mean (±95% CI) Change from Baseline Concentration-time Profiles for Serum Cytokines - Pharmacodynamic Analysis Set

A plot similar to Figure 14 4 2 3 will be presented for change from baseline values

<Programming Note: Present for all cytokines analytes with units Analytes: IL-4, IL-5, IL-13, IL-33, and sST2 >

\\ieedc-vnasc01\biosdata\AnaptysBio\ANB020\CYA74392\Biostatistics\Documentation\SAP\Final\20181218 Document: Author:

> 18Dec2018 Version Date:

1.0

Version Number:

[figure not shown]
29 June 2020 158

AnaptysBio Inc. PROTOCOL ANB020-004 Page 17 of 19

Figure 14 4 2 5

Mean (±95% CI) for Ex-vivo IFN-gamma – Pharmacodynamic Analysis Set

CI = confidence interval

Document: Author:

CONFIDENTIAL

Clinical Study Report ANB020-004 - Original

AnaptysBio Inc.
PROTOCOL ANB020-004
ells
Page 18 of 19

Figure 14 4 2 6

Mean (±95% CI) Change from Baseline for Ex-vivo IFN-gamma – Pharmacodynamic Analysis Set

A plot similar to Figure 14 4 2 5 will be presented for change from baseline values

Document: \\ieedc-vnasc01\\biosdata\AnaptysBio\ANB020\CYA74392\Biostatistics\Documentation\SAP\Final\20181218 Author:

29 June 2020 160

Version Number:

Version Date:

1.0 18Dec2018

[figure not shown]

Figure Shells

AnaptysBio Inc. PROTOCOL ANB020-004 Page 19 of 19

Figure 14 4 2 7

Scatter Plot of Observed Eosinophil Count versus Serum ANB020 Concentration - Pharmacodynamic Analysis Set

Figure 14 4 2 8

Scatter Plot of Observed Serum Cytokine Levels versus Serum ANB020 Concentration - Pharmacodynamic Analysis Set

Note: All available cytokines will be presented on separate plots

Figure 14 4 2 9

Scatter Plot of Observed Ex-vivo IFN-gamma Levels versus Serum ANB020 Concentration - Pharmacodynamic Analysis Set

Version Date: 18Dec2018

Version Number:

1.0

Document Approval Signature(s)

This document has been signed electronically in compliance with Quintiles electronic signature policies and procedures. This page is a manifestation of the electronic signatures, which may be confirmed within the Quintiles source system in accordance with Quintiles records retention policies.

Note: the Title field in the signature block has been intentionally left blank.

UserName: Title: Date: Thursday, 20 December 2018, 10:54 AM Meaning: I Approve the Document	Eastern Time
UserName: Title: Date: Thursday, 20 December 2018, 11:05 AM Meaning: I Approve the Document	Eastern Time
UserName Title: Date: Thursday, 20 December 2018, 11:34 AM	Eastern Time

Meaning: I Approve the Document

Biostatistics File Note Page 1 of 5

Section A

Customer: AnaptysBio, Inc.

Project Code: CYA74392

Protocol Number: ANB020-004

Title of Note:

Additional analyses outside the scope of final SAP (Version Date:

18DEC2018)

Section B

DESCRIPTION:

Form No.: CS_FM_BS020 Revision 3 Reference: CS_OP_BS001

Effective Date: 12Nov2017

Copyright © 2010, 2012, 2017 IQVIA. All rights reserved. The contents of this document are confidential and proprietary to IQVIA Holdings Inc. and its subsidiaries. Unauthorized use, disclosure or reproduction is strictly prohibited.

CONFIDENTIAL

Biostatistics File Note Page 2 of 5

Background

The note-to-file (NTF) is intended to document the additional analyses that are outside the scope of the final SAP dated 18DEC2018.

Objective

The objective of the additional analysis is to assess the reduction in asthma control questionnaire (ACQ) 5 score relative to the scheduled study time points including day 8, 22, 36, 64, 85, 106 and end of study (EOS) visit.

Endpoint

The endpoint of the additional analysis is ACQ-5 score and its percent change from baseline relative to scheduled study time points.

Analysis Set

Full analysis set (FAS), as defined in the SAP dated 18DEC2018, will be used for the analysis.

Analysis Method

The analyses will be performed descriptively using n (number of subjects with non-missing values), mean, standard deviation (SD), median, minimum and maximum as summary statistics. Additionally, 95% confidence interval (CI) for mean will also be provided.

The above mentioned summary statistics and 95% Cl's for mean using classical method will be provided for both observed and percent change from baseline relative to different scheduled visits for ACQ-5 score. Summaries for screening and baseline will be provided for the observed values only.

Number of subjects within each treatment group under FAS (N) will also be reported along with summary statistics for the analysis.

A line plot for mean (± SD) percent change from baseline for ACQ-5 score will be provided for each of the treatment groups against the applicable scheduled study visits.

A listing detailing the individual ACQ component scores along with ACQ-5 score will be presented for each visit of data collection along with demographic characteristics such as age and gender for each subject as applicable.

Derivation

ACQ-5 score will be derived by summing the 5 individual scores, as described in Table 1, and utilizing the average for each subject at each applicable visit. A percentage of change from baseline was then assessed.

Symptoms will be scored on a scale of 0 to 6 with 6 being the worst case. ACQ-5 will be missing if any individual score is missing.

Table 1: Individual components and corresponding responses for calculating ACQ-5 score

Individual item	Response
1. On average, during the past week, how	0 Never
often were you woken by your asthma	1 Hardly ever
during the night?	2 A few times
	3 Several times

Form No.: CS_FM_BS020 Revision 3 Reference: CS_OP_BS001

Effective Date: 12Nov2017

Copyright © 2010, 2012, 2017 IQVIA. All rights reserved. The contents of this document are confidential and proprietary to IQVIA Holdings Inc. and its subsidiaries. Unauthorized use, disclosure or reproduction is strictly prohibited.

Biostatistics File Note Page 3 of 5

	4 Many times	
	5 A great many times	
	6 Unable to sleep because of asthma	
2. On average, during the past week, how	0 No symptoms	
bad were your asthma symptoms when	1 Very mild symptoms	
you woke up in the morning?	2 Mild symptoms	
	3 Moderate symptoms	
	4 Quite severe symptoms	
	5 Severe symptoms	
	6 Very severe symptoms	
3. In general, during the past week, how	0 Not limited at all	
limited were you in your activities	1 Very slightly limited	
because of your asthma?	2 Slightly limited	
	3 Moderately limited	
	4 Very limited	
	5 Extremely limited	
	6 Totally limited	
4. In general, during the past week, how	0 None	
much shortness of breath did you	1 A very little	
experience because of your asthma?	2 A little	
	3 A moderate amount	
	4 Quite a lot	
	5 A great deal	
	6 A very great deal	
5. In general, during the past week, how	0 None	
much of the time did you wheeze?	1 1-2 puffs/inhalations most days	
	2 3-4 puffs/inhalations most days	
	3 5-8 puffs/inhalations most days	
	4 9-12 puffs/inhalations most days	
	5 13-16 puffs/inhalations most days	
	6 More than 16 puffs/inhalations most days	

Further action required:

Form No.: CS_FM_BS020 Revision 3 Reference: CS_OP_BS001

Effective Date: 12Nov2017

Copyright © 2010, 2012, 2017 IQVIA. All rights reserved. The contents of this document are confidential and proprietary to IQVIA Holdings Inc. and its subsidiaries. Unauthorized use, disclosure or reproduction is strictly prohibited.

CONFIDENTIAL

Biostatistics File Note Page 4 of 5

List of outputs

Below is the list of outputs that will be produced for the proposed analysis on ACQ-5.

Table 1: Asthma Control Questionnaire (Summary of Scores for ACQ-5) - Full Analysis Set

Listing 1: Asthma Control Questionnaire (ACQ-5) - Full Analysis Set Figure 1: Mean (±SD) % change from baseline of ACQ-5 score by visit

Programming Note:

One ADaM dataset "ADQS_AD" will be created by modifying the program of already existing dataset "ADQS". "ADQS_AD" will have all the variables as in "ADQS" with only below mentioned additional information under "**Programing logic for "ADQS_AD"**".

The newly created outputs and dataset mentioned in this NTF and their programs will be stored in the respective study folders as in the main analysis for this project.

Programing logic for "ADQS_AD":

If ACQ-5 individual item are non-missing, then populate

PARAM="ACQ5 Score";

PARAMCD="ACQ5";

AVAL=5 Average of 5 individual ACQ-5 items if all the individual items are non-missing; else set the value of AVAL to missing if at least one individual item score is missing.

PARAMN=9; PARCAT2="Asthma Control Questionnaire";

AVALC=character result of AVAL;

ABLFL= "Y" (for baseline value, else populate as blank);

BASE=Populate the baseline value:

BASEC=Character result of BASE;

CHG=Post baseline - Baseline;

PCHG= [(Post baseline - Baseline)*100]/Baseline if non-zero baseline (BASE ne 0); else set the value of PCHG to missing if BASE = 0;

Section C

AUTHOR:

^..........

(Print Name):	Signature (Sign):	
Job Title:	 Date:	
Reviewer:		
Signature (Print Name):	Signature (Sign):	
Job Title:	 Date:	

Form No.: CS FM BS020 Revision 3 Reference: CS OP BS001

Effective Date: 12Nov2017

Copyright © 2010, 2012, 2017 IQVIA. All rights reserved. The contents of this document are confidential and proprietary to IQVIA Holdings Inc. and its subsidiaries. Unauthorized use, disclosure or reproduction is strictly prohibited.

IMS Health & Quintiles are now IMS Health & Quintiles are now

Biostatistics File Note			Page 5 of 5
Approver:			
Signature (Print Name):		Signature (Sign):	
Job Title:	AnaptysBio, Inc	Date:	

Form No.: CS_FM_BS020 Revision 3 Reference: CS_OP_BS001

Effective Date: 12Nov2017

Copyright © 2010, 2012, 2017 IQVIA. All rights reserved. The contents of this document are confidential and proprietary to IQVIA Holdings Inc. and its subsidiaries. Unauthorized use, disclosure or reproduction is strictly prohibited.

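### The added ACQ-5 analysis summarises change only as percent of baseline, so one low-baseline patient can dominate or reverse an arm mean; the absolute change it already derives appears in no described output

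*SAP*

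**What the plan says.** The note, which documents analyses outside the final SAP, defines its endpoint as follows: "The endpoint of the additional analysis is ACQ-5 score and its percent change from baseline relative to scheduled study time points". On the scale it says "Symptoms will be scored on a scale of 0 to 6 with 6 being the worst case", and its programming logic gives "AVAL=5 Average of 5 individual ACQ-5 items if all the individual items are non-missing".

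The summary statistics are n, "mean, standard deviation (SD), median, minimum and maximum as summary statistics", plus a 95% CI for the mean by the classical method. They "will be provided for both observed and percent change from baseline relative to different scheduled visits for ACQ-5 score". The only figure is "Figure 1: Mean (±SD) % change from baseline of ACQ-5 score by visit". The listing covers item scores and the ACQ-5 score.

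The programming logic also derives absolute change, "CHG=Post baseline - Baseline". For percent change it divides by baseline, with the rule "else set the value of PCHG to missing if BASE = 0". None of the three described outputs (table, listing, figure) is said to show absolute change.

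The main SAP works differently. Section 6.6 defines change as visit value minus baseline value. Section 17.3.1.1 and table shell 14.2.3.1 report ACQ as observed value and absolute change.

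**The concern.** Percent change on a short bounded scale is asymmetric. It has a floor for improvement, almost no ceiling for worsening when the baseline is small, and no value at a baseline of zero. A clinically modest rise from a low baseline becomes a change of several hundred percent, and in a small arm it can outweigh the results of everyone else. A patient who starts at zero and worsens disappears from the percent-change summary.

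At stake is how readable the ACQ-5 result is. The arm mean, its 95% CI and the mean (±SD) plot could all be governed by one patient. The quantity that would not behave this way is computed but not tabulated. ACQ-5 would also be reported on a different change scale from ACQ-7, although both come from the same questionnaire.

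**Working it through.** The documents give no ACQ-5 effect, variance or sample size figure, so there is nothing to reproduce. The check applies the note's own formulas to a hypothetical arm.

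**Inputs from the documents**
- Five items, each 0 to 6, averaged (file note): steps of 1/5 = 0.2; smallest non-zero baseline 0.2; maximum 6.
- CHG = post - baseline; PCHG = 100 × (post - baseline)/baseline, missing if baseline = 0 (file note).
- 12 patients per arm (Protocol 6.2.2).
- No minimum ACQ among the entry criteria (Protocol 4.3.1).

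**Assumptions, not in the documents**
- Eleven patients go from 2.4 to 1.8. The twelfth starts low and worsens.
- The classical interval is taken as the t interval.

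**Range of PCHG**
- Largest possible worsening: 100 × (6 - 0.2)/0.2 = +2900%.
- Largest possible improvement: -100%.

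**One low-baseline patient, 0.2 to 1.2**
- Each of the eleven: CHG -0.6, PCHG 100 × (-0.6)/2.4 = -25%.
- The twelfth: CHG +1.0, PCHG 100 × 1.0/0.2 = +500%.
- Mean PCHG = (11 × -25 + 500)/12 = 225/12 = +18.8%; SD 151.6; 95% CI -77.5 to 115.0. The median stays at -25.0%.
- Mean CHG = (11 × -0.6 + 1.0)/12 = -5.6/12 = -0.47; 95% CI -0.76 to -0.17.

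The mean percent change has the opposite sign from the absolute change, although 11 of 12 patients improved.

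**How far this depends on the baseline, for a 1.0-point rise in the twelfth patient**

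| Baseline | PCHG, twelfth patient | Mean PCHG | Mean CHG |
|---|---|---|---|
| 0.2 | +500% | +18.8% | -0.47 |
| 0.4 | +250% | -2.1% | -0.47 |
| 0.6 | +166.7% | -9.0% | -0.47 |
| 0.8 | +125% | -12.5% | -0.47 |
| 1.0 | +100% | -14.6% | -0.47 |

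The sign reverses only if the twelfth patient's PCHG exceeds 11 × 25 = 275%, that is, a rise above 2.75 × baseline. This is 0.55 points from 0.2, 1.1 from 0.4, 1.65 from 0.6 and 2.75 from 1.0.

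**Zero baseline, 0 to 1.0**
- PCHG: n = 11, mean -25.0%. The worsening is not counted.
- CHG: n = 12, mean -0.47.

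**The case against.** The strongest reply is that the scenario is undocumented and that the note already contains safeguards. Entry requires severe asthma, an exacerbation in the past 12 months, pre-bronchodilator FEV1 below 80% and high-dose ICS plus LABA, which makes near-zero scores less likely. The table gives n, median, minimum and maximum as well as the mean, so an extreme value would show. Observed scores are summarised at every visit with a 95% CI. The zero rule is explicit and avoids an undefined ratio. The SAP also reports absolute change for ACQ-7, which contains all five ACQ-5 items.

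Much of this stands. The risk is a possibility, and the median in the worked example is unaffected. Three things remain. The FEV1 criterion does not bound ACQ-5, because ACQ-5 omits the FEV1 item. Protocol Appendix IV counts as severe some asthma that is kept controlled by Step 4 or 5 treatment, so patients with few current symptoms can qualify. And the difference in observed means gives mean change only roughly, without its SD or CI.

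Three stronger readings are tempting but not supported:
- **Patients are dropped from the analysis.** Zero-baseline patients leave only the percent-change summary. They stay in the observed-score summary and the listing.
- **Percent change costs power.** The note plans no between-arm test, and the study is not sized on power. Which scale is more sensitive depends on whether the effect is additive or proportional, and the documents support neither.
- **A model-based comparison is missing.** The note is descriptive by design; adding an MMRM would go beyond its scope.

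**Conclusion.** The point holds as a minor reporting weakness. In this note, change in ACQ-5 is summarised only as percent change, and at 12 per arm one patient with a baseline of 0.2 who worsens by 1.0 point can move an arm mean from -25.0% (all twelve at 2.4 to 1.8) to +18.8%. The effect fades quickly: at a baseline of 1.0 the same rise leaves the mean at -14.6%. These figures rest on an invented arm, and the actual baseline ACQ-5 values are not in the documents. A reader might infer that the ACQ-5 result is distorted; the documents show only that the chosen measure allows it. No primary or secondary conclusion is affected.

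**What to change.** In the file note's Table 1, add absolute change by visit with the statistics already listed (n, mean, SD, median, minimum, maximum, 95% CI), and plot absolute change in Figure 1. This matches the SAP's handling of ACQ-7 and measures directly the reduction that the note sets out to assess. Keep percent change, if at all, as a secondary summary, and state the number of zero baselines excluded in each arm.

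The cost is one extra set of table columns and a different variable in one figure. The derivation is already specified, and no new data or model is needed.
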